Study Protocol Needle-free Sensing of Blood Glucose

Coordinating Investigator (CI): [name]

Co-investigators: [name], [name], [name], [name], [name]

1. Background

Diabetes is diagnosed in 5.8% of the population of New Zealand, and disproportionately affects lower socioeconomic status groups, as well as Māori, Pacific, and Asian peoples [1]. Type 1 and insulin dependent type 2 diabetics require injections of insulin multiple times per day to manage the glucose concentration in their blood. The appropriate dose of insulin is determined using a measurement of blood glucose concentration that typically requires the fingertip be pricked with a lancet. The drop(s) of blood resulting from this prick are used to perform the glucose measurement. In an effort to make this process easier for diabetics, we are investigating whether this testing can be achieved with, and integrated into, a needle-free jet injection device. Performing this process without a needle/lancet will avoid the associated issues of sharps waste, accidental needle stick, and needle-phobia [2].

Needle-free jet injection is an established method of transdermal drug delivery. The technique involves the liquid drug being formed into a high speed jet which is capable of penetrating the skin, thus removing the need for a needle. Jet injection has been shown to be an effective delivery method for vaccines, insulin, hormones, and anaesthetics, among others [2], [3]. In many studies, the pain and discomfort associated with a jet injector has been shown to be similar to that experienced with the equivalent needle based injection [2].

While blood extraction with a jet injector has not yet been trialled, one study investigated the ability of a jet injector to extract interstitial fluid [4]. This study attempted to collect the fluid back through the same small orifice through which the jet was formed, and waited less than 0.5 seconds between breaking the skin and collecting the fluid. The volume of fluid collected ranged between 10 μ L and 40 μ L but was found to be mainly derived from the fluid that was injected, with interstitial fluid making up between 1% and 3%. As demonstrated by this study, we anticipate that one of the major problems with obtaining a capillary blood sample using jet injected fluid. As part of this study we wish to investigate the extent of this dilution issue. We propose to measure the dilution by marking our injected fluid with indocyanine green (ICG), an FDA approved fluorescent marker. By exciting the retrieved blood samples with 780 nm light, and measuring the resulting fluorescence we will be able to measure the dilution of the sample.

ICG is commonly used for diagnostic purposes (e.g., cardiocirculatory, retinal and liver function diagnostic tests), typically at a dose of no more than 2 mg/kg and a concentration of 5 g/L [5]. ICG has been delivered transdermally into the subcutaneous tissue in multiple fluorescent lymphography studies, and into the dermal layer in a recent study performing fluorescent microscopy. Delivery of 20 μ L of 5 g/L ICG into the dermis was described as having a "short-time tolerable burning sensation" [6], but in this study we plan to use a concentration of only 10 mg/L.

2. Research Aims

In this study we intend to use needle-free jet injection not to deliver a drug, but instead just to pierce the skin with a small volume of isotonic saline or ICG solution, and then retrieve a capillary blood sample. Ultimately we believe a single jet injection device may be able to extract blood, perform a blood glucose measurement and then, based on this measurement, deliver the ideal volume of insulin. However, this study will focus only on establishing the ability of this technique to achieve a measurement of blood glucose concentration.

This work will test the ability of a needle-free jet injection device to release capillary blood in order to measure glucose concentration. We wish to evaluate how this technique compares to the current best practice where the skin is broken with a lancet. We will compare jet injections performed with a standard circular orifice and two custom orifices that produce jets of rectangular shape ('slot' orifices). The custom slot orifices are designed to mimic the shape of the puncture made by a lancet in the skin, and we hypothesise that this may assist in obtaining a blood sample with the jet injector. The comparisons will require measurement of the volume of blood released, blood sample dilution, blood glucose concentration, and participant discomfort.

2.1. Principal Research Question

"Can a needle-free jet injection device be used to obtain a capillary blood sample for a glucose concentration measurement?"

This can be broken down into five further questions which relate directly to the measurements we will be making:

- a) Does a jet injector release a similar volume of capillary blood relative to a lancet?
- b) Does the use of a jet injector dilute the capillary blood sample, and, if so, how does this dilution change over time as blood is released?
- c) Does a slot orifice help release more blood than a circular orifice? And is the dilution of the collected blood different for jet injection with a slot orifice versus a circular orifice?
- d) Is the use of a jet injector for this purpose associated with similar, or lesser, levels of discomfort relative to a lancet?
- e) Does a jet injection lead to any significantly different skin reactions at the intervention site relative to a lancet prick?

3. Research Methods

3.1. Study Design Overview

This is a pilot study aiming to assess the feasibility of using a jet injector in the place of a lancet when retrieving a capillary blood sample. Each participant in the study will receive four interventions: the current best practice for capillary blood sampling (a lancet prick), a jet injection with a standard circular orifice, and two jet injections with different custom slot orifices. This study is designed to be single-blinded and all participants will serve as their own control as each participant will receive the lancet based sampling. Participants will be aware they are receiving one of each intervention, but will be blinded to the order and identity of which intervention is occurring at which site. The study will be conducted in the ground floor laboratory space (G20) of the Auckland Bioengineering Institute ([name]).

3.2. Population & Recruitment

We intend to recruit up to 35 healthy participants to take part in this study. These participants will be divided into two groups with up to 25 participants in the first group and up to 10 in the second. The difference between these groups relates to the measurements that will be made on their blood samples, and also in the injectate used to obtain these measurements. The samples gathered from participants in the first group, using isotonic saline for the jet injections, will be tested for glucose concentration, while those from the second group, using isotonic saline with ICG for the jet injections, will have a fluorescent based dilution measurement. Participants will be aware that the study is structured in this way, and will be aware of which group they are being recruited into.

With a minimum sample size of 20 in the first group we predict we will be able to distinguish statistically significant differences between groups whose mean dilution differs by as little as 10% ($\sigma_{glucometer}$ =0.6 mmol/L, α =0.05, β =0.1). We predict we will be able to observe differences in mean dilution as low as 5% in group 2 with a sample size of at least 8 ($\sigma_{fluorimeter}$ =3%, α =0.05, β =0.1). Sample volume is measured identically across both groups and we predict we will be able to observe differences in mean volume released as low as 0.84 µL ($\sigma_{BloodVolume}$ =1 µL, α =0.05, β =0.1).

The study will be advertised within the Auckland Bioengineering Institute and Department of Engineering Science. This will involve flyers posted within Auckland Bioengineering House ([name]) and an email sent to the Auckland Bioengineering Institute. These advertising materials will recommend that anybody interested in participating get in contact with the researchers for more information. In response to expressions of interest the researchers will provide a copy of the participant information sheet (PIS) and consent form (CF) to give detailed information about the study. Participants will be asked to take their time reading these forms and, if they are interested in participating, to indicate times that might suit them to come in for the study. This will also allow potential participants adequate opportunity to ask questions and seek external advice regarding participation in the study.

Participants will be required to visit the Auckland Bioengineering Institute for one 45 minute session where the interventions will take place. The participants will be asked to complete a short questionnaire 24 hours after the interventions, and send a photograph of the fingertips to the researchers.

We will aim for gender and ethnic representation in proportion with the greater New Zealand population. We imagine we will be able to get the required number of participants from within the Auckland Bioengineering Institute and Department of Engineering Science. However, if this proves more difficult than expected we will extend the recruitment to the wider University (UoA) using the same flyers and emails.

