3.6. Measurements

Volume

The blood will be collected from the skin using capillary tubes. As the dimensions of these capillary tubes are known the sample volume will be measured by the length of tube that is filled with blood.

Group 1: Glucose Concentration

For the samples collected on participants from group 1 we will then measure the glucose concentration of each blood sample. This will be done using a CareSens N point of care glucometer. This approved (and Pharmac funded) device involves the blood sample being collected onto a single use test strip inserted into the glucometer. The dilution of the blood samples collected following the jet injections will be implied by comparing the glucose concentration with that measured on the control (lancet) samples. The blood samples will be disposed of as medical waste following this glucose measurement.

Group 2: Blood Dilution (Fluorescence)

For group 2 after the volume is measured, we will measure the ICG concentration in the sample using a benchtop fluorimeter that has been developed at the Auckland Bioengineering Institute specifically for this purpose. The capillary tube containing the blood sample will be placed into the fluorimeter, which will excite the sample with 780 nm light. The resulting fluorescence will be measured, indicating the concentration of ICG and hence the proportion of injectate in the blood sample.

As the fluorimeter requires a sample of 10 μ L to produce a reliable measurement, and we expect our samples to typically be around 5 μ L, we will pre-mix the samples with isotonic saline solution. We will mix a volume of saline rounded up to the nearest 1 μ L with our sample to ensure a total volume of at least 10 μ L. In samples where the initial volume is greater than 5 μ L the added volume of saline will be equal to the sample volume rounded up to the nearest 1 μ L. This will ensure all samples will end up in the ideal concentration range of 0 mg/L – 5 mg/L for measurement of ICG with this device. The samples will be weighed following this mixing to quantify the volume that was added. The fluorescence measurement, initial sample volume, and mixed volume will then be used to calculate the ICG concentration, and therefore the blood volume, in the initial sample.

Perceived Pain

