3.9. Safety Monitoring

An internal safety monitoring committee will review the data collected during the trial looking for evidence of adverse effects or unexpected risks to participants or researchers. The committee will be particularly interested in any evidence of unexpected behaviour from the jet injections, or lasting symptoms at the intervention sites. The trial will be terminated at the discretion of the committee if evidence of these issues were to arise. The committee will consist of three members of the research team: [name], [name], [name], as well as the health care professional hired to oversee the blood sampling procedures. This committee will meet every fortnight, assuming around 3 participants per week complete the trial, or more regularly as necessary.

Elevated pain scores, bruising, and excessive bleeding have all been identified as signs of unexpected behaviour from the jet injections. Extreme levels of pain will be measured as an average pain score of >7.5 after at least 5 participants. If evidence of unexpected adverse effects (e.g. infection, nerve damage, etc.) are observed in the participant feedback and "day after" photos the study will be terminated.

If the average glucose measurement in the control samples (lancet) suggest the participant had an extreme glucose concentration (less than 4.0 mmol/L or greater than 11.1 mmol/L) at the time of sampling, the participant will be contacted to describe this measurement, and encourage the participant to talk to their GP.

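### The Group 1 power claim (10% dilution difference, n = 20, 90% power) does not follow from its stated inputs; on the best-supported reading it needs a mean glucose of about 6.2–6.5 mmol/L or more

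*Protocol*

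**What the plan says.** Protocol section 3.2 gives three precision statements. The Group 1 statement opens "With a minimum sample size of 20 in the first group we predict" and continues "we will be able to distinguish statistically significant differences between groups whose mean dilution differs by as little as 10"%. Its inputs are an SD subscripted as the glucometer's, with "0.6 mmol/L, α =0.05, β =0.1". Recruitment is "up to 25 participants in the first group and up to 10 in the second".

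The Group 2 statement beside it has effect and SD in the same unit: 5% with an SD of 3%, at least 8 participants, and the same alpha and beta.

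Section 3.6 says that Group 1 dilution "will be implied by comparing the glucose concentration with that measured on the control (lancet) samples". Section 3.1 makes each participant their own control. Section 3.5 collects four samples per intervention, at 10, 20, 30 and 40 s.

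The only glucose values in the protocol are the notification limits in section 3.9: "extreme glucose concentration (less than 4.0 mmol/L or greater than 11.1 mmol/L".

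**The concern.** A 10% difference can be set against an SD of 0.6 mmol/L only after multiplying it by a mean glucose, and the protocol gives none. It also does not say whether 0.6 is the SD of one reading or of a within-person difference, whether the test is paired, or whether it is one- or two-sided. The claim is therefore not derivable from the inputs printed with it.

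The label ties the SD to the instrument. If so, it leaves out variation between people in how much a jet dilutes the sample, and any drift in glucose across the four sequential interventions. Both would widen the SD of a jet-minus-lancet difference.

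Glucose-implied dilution is Group 1's measure for research questions (b) and (c). If the achievable resolution is coarser than 10%, a non-significant comparison could be taken to exclude a 10% dilution when it does not.

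**Working it through.** **Inputs.** From section 3.2: n = 20, SD 0.6 mmol/L, alpha 0.05, power 0.90. Two-sided testing is assumed. Mean glucose is not given, so it is varied as an assumption.

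**Step 1: which formula did the protocol use?** Test it on Group 2, where the units agree. The per-arm two-sample normal formula is n = 2(z₀.₉₇₅ + z₀.₉₀)² × SD²/δ², with z₀.₉₇₅ + z₀.₉₀ = 3.2415.
- Two-sample: 2 × 10.507 × 9/25 = 7.57, rounded up to 8. This is the stated figure.
- SD read as that of the within-person difference: 10.507 × 9/25 = 3.78, so 4 (7 with a t correction). Neither is 8.

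The match is not unique. A one-sided paired t test with a per-reading SD also gives 8. The volume statement (0.84 µL, SD 1 µL) cannot decide the matter because no n is given. The two-sample formula gives 0.837 at n = 30, 0.866 at the stated minimum total of 28 and 0.775 at the maximum of 35.

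**Step 2: detectable difference in Group 1 for a single-time-point contrast, n = 20, two-sided.** Dividing by 0.10 gives the mean glucose at which it equals 10%.

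| Reading of 0.6 and test | Detectable (mmol/L) | Mean needed (mmol/L) |
|---|---|---|
| Two-sample z: 3.2415 × 0.6 × √(2/20) | 0.615 | 6.15 |
| Two-sample t | 0.631 | 6.31 |
| Paired t, SD 0.6 × √2 = 0.849 | 0.649 | 6.49 |
| 0.6 is the SD of the difference, z: 3.2415 × 0.6/√20 | 0.435 | 4.35 |
| 0.6 is the SD of the difference, paired t | 0.459 | 4.59 |

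One-sided with a per-reading SD gives 0.555 (z) to 0.576 (paired t), so a mean of 5.55–5.8. With all 25 recruited (two-sided, per-reading) it is 0.550 to 0.574, so 5.5–5.7.

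**Step 3: power for a true 10% at n = 20, by assumed mean glucose.**

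| Assumed mean (mmol/L) | Two-sample z | Two-sample t | Paired t, SD 0.849 | Paired t, SD 0.6 |
|---|---|---|---|---|
| 4.5 | 66% | 64% | 61% | 89% |
| 5.0 | 75% | 73% | 71% | 94% |
| 5.5 | 83% | 81% | 79% | 97% |
| 6.2 | 90.5% | 89% | 87% | 99% |
| 6.5 | 93% | 92% | 90% | >99% |
| 7.0 | 96% | 95% | 94% | >99% |

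At an assumed 5.0 mmol/L the detectable difference on the per-reading rows is 0.615/5 = 12.3% to 0.649/5 = 13.0%.

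**Step 4: using the repeated readings.** These figures assume independent reading errors and lancet glucose that is flat from 10 to 40 s.
- One jet reading against the mean of four lancet readings: SD = 0.6 × √(1 + 1/4) = 0.671. The paired t detectable difference is 0.513 mmol/L, or 10.3% at an assumed 5.0, with 88.5% power for 10%.
- Four readings averaged in both arms: SD = 0.6 × √(2/4) = 0.424. The detectable difference is 0.324 mmol/L, or 6.5% at an assumed 5.0.

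**Step 5: what the instrument-only SD leaves out.** Assume, for illustration, a true between-person SD of 0.5 mmol/L in the difference, and scale each detectable difference by its SD.
- Single readings: √(0.72 + 0.25) = 0.985, and 0.649 × 0.985/0.849 = 0.753 mmol/L, or 15% at 5.0.
- Averaged lancet reference: √(0.45 + 0.25) = 0.837, and 0.513 × 0.837/0.671 = 0.640 mmol/L, or 12.8%.
- Averaging in both arms: √(0.18 + 0.25) = 0.656, and 0.324 × 0.656/0.424 = 0.501 mmol/L, or 10.0%.

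**The case against.** The strongest reply is that no error is shown. A planning mean of about 6.2 mmol/L makes the stated figure correct under the two-sample z formula. That value lies inside the 4.0–11.1 mmol/L limits of section 3.9, and the protocol states no fasting requirement. Because the design is own-control, 0.6 could be meant as the SD of the within-person difference, in which case 10% holds from about 4.4–4.6 mmol/L. The claim speaks of mean dilution, so it could also refer to the average over the four time points, which would meet it comfortably on instrument error alone. Finally, this is a feasibility pilot, and how the lancet reference is formed is normal material for an analysis plan.

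Much of this stands. A reader might infer that the 90% power is missed, or that the sentence contains an arithmetic error. The protocol supports neither, because the mean glucose is simply absent. The 5.0 and 5.5 mmol/L rows are assumptions, not facts about this population. Nor does the protocol say that a null result would be read as excluding 10%.

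Three things remain. The sentence prints a claim with its inputs, and the inputs do not yield it; an analysis plan does not cure that. Reading 0.6 as the SD of a difference conflicts with the instrument label and, by the same reasoning, does not reproduce Group 2's n of 8. The averaging rescue works as described only if reading errors are independent and dilution does not vary between people.

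**Conclusion.** The concern holds as a claim that cannot be verified, with a conditional shortfall. On the best-supported reading (per-reading SD, two-sided, single time point), n = 20 detects 0.615–0.65 mmol/L with 90% power, and 10% is reached only from a mean of about 6.2–6.5 mmol/L. If the mean were 5.0 or 5.5 mmol/L, power for 10% would be about 71–75% or 79–83%; at 6.5 it would be 90–93%.

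The threshold depends on the reading. It falls to about 5.6–5.8 if one-sided, about 5.5–5.7 if all 25 are recruited, and about 4.4–4.6 if 0.6 is the SD of the difference. Whichever reading was meant, if the SD is instrument error only, the resulting detectable difference is a lower bound. The point deserves correction before results are interpreted, but does not call the design into question.

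**What to change.** In section 3.2, state the assumed mean glucose (or give the SD as a percentage), say whether 0.6 is the SD of a reading or of a within-person difference, and name the test and its sidedness. Say whether the claim concerns one time point or the average of four. Restate the detectable difference to match, for example about 12–13% if the mean is 5 mmol/L and the contrast uses single readings. Mark it as a lower bound, since between-person variation in dilution and glucose drift are left out.

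Use each participant's mean of the four lancet readings as the reference for the jet samples. Section 3.9 already averages the lancet samples for the notification rule. This lowers the SD from 0.85 to 0.67 and brings the jet-versus-lancet figure to about 10.3% at an assumed 5 mmol/L. It does not help comparisons between orifices at a single time point, where the shared reference cancels and the figure stays near 13%.

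The cost is a reworded sentence and one analysis definition, with no extra participants. The stated resolution may look less favourable. The averaged reference assumes that lancet glucose is flat from 10 to 40 s and that reading errors are independent; the flatness can be checked in the trial's own lancet data.

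### Group 2's 5% detectable difference at n = 8 takes the fluorimeter's 3% as the whole SD and uses a normal approximation; for the back-calculated dilution it is a best case and should be restated.

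*Protocol*

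**What the plan says.** Section 3.2 sizes Group 2 to observe "differences in mean dilution as low as 5% in group 2 with a sample size of at least 8". The inputs in brackets are a fluorimeter SD and error rates: "3%, α =0.05, β =0.1". Recruitment is "up to 25 participants in the first group and up to 10 in the second", so 8 is a floor and 10 the ceiling. Section 3.1 makes the comparison within participants: "all participants will serve as their own control as each participant will receive the lancet based sampling".

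Section 3.6 describes how a Group 2 dilution value is obtained. The fluorimeter needs 10 µL, but "we expect our samples to typically be around 5 μ L, we will pre-mix the samples with isotonic saline solution". Samples of 5 µL or less are made up to at least 10 µL in total. For larger samples "the added volume of saline will be equal to the sample volume rounded up to the nearest 1" µL. The value for the original sample is then derived: "The fluorescence measurement, initial sample volume, and mixed volume will then be used to calculate the ICG concentration".

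The protocol does not say whether the 3% is in percentage points, relative to the reading, or a share of the measuring range. Nor does it say whether the 3% applies before or after the back-calculation.

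**The concern.** The SD in the sample-size statement carries the instrument's label, but the quantity compared is not the instrument's reading. It is the reading multiplied by a mixing factor, which is itself built from two measured volumes. An instrument SD equals the SD of that quantity only under particular assumptions, and the protocol states none of them. With 8 participants, the choice between a normal and a t calculation also matters.

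Group 2 is the only direct measurement of dilution and serves research questions (b) and (c) in section 2.1. If the stated 5% is optimistic, a null comparison between orifices could be read as ruling out a 5% difference when the design did not have the stated power to detect one.

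**Working it through.** **Inputs.** Difference 5%, SD 3%, α = 0.05, β = 0.1, n = 8 to 10 (section 3.2). Four interventions per participant (section 3.1). Mixing rule and 0–5 mg/L measuring range (section 3.6). Injectate ICG 10 mg/L (section 3.4, Jet Injection, and section 3.7). The opening paragraph of section 3.4 gives a different concentration, and those passages need reconciling. Here 10 mg/L is only an input to one scenario.

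**1. Reproducing the plan.** Two-sided two-sample normal formula: (1.960 + 1.282) × 3 × √(2/8) = 3.2415 × 1.5 = 4.86%. The n for a 5% difference is 8, and power at n = 8 is Φ(5/1.5 − 1.960) = Φ(1.373) = 91.5%. The plan's figure is reproduced with 3% used unchanged as the whole SD. (One-sided, n would be 7.)

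**2. Same SD, t-based.** For two independent samples the standard error is 3 × √(2/8) = 1.5. For pairs with SD of differences 3√2 it is 3√2/√8 = 1.5. The noncentrality is 5/1.5 = 3.33 in both cases; only the degrees of freedom differ (14 and 7).

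| SD 3, one sample per intervention | Detectable at 90% power | Power for 5% |
|---|---|---|
| n = 8, normal | 4.86% | 91.5% |
| n = 8, two-sample t | 5.23% | 87.2% |
| n = 8, paired t | 5.69% | 81.5% |
| n = 10, two-sample t | 4.60% | 94.1% |
| n = 10, paired t | 4.90% | 91.1% |

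**3. The mixing factor.** Let D = mixed volume / initial volume. For 5 µL, add 5 (D = 2); for 4 µL, add 6 (D = 2.5); for 2 µL, add 8 (D = 5). Above 5 µL, D runs from 2.0 to about 2.1. So D is at least 2 for every sample handled as section 3.6 describes. (Section 3.7 has the Group 2 tubes going straight into the fluorimeter and does not mention mixing.) The original value is reading × D, so errors in either volume enter through D in addition to the reading error.

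**4. What scaling does to 3%.**

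- *Additive, in points of injectate fraction, on a single mixed reading.* At D = 2 the SD is 3 × 2 = 6 points. At n = 8 the detectable difference is 9.7% (normal), 10.5% (two-sample t) or 11.4% (paired t, SD of differences 6√2), with power for 5% of 38%, 34% and 30%. At n = 10 it is 8.7% to 9.8%, with power of 46% to 38%. At D = 2.5 (a 4 µL sample) the SD is 7.5 points.
- *A share of the 0–5 mg/L range.* 3% × 5 = 0.15 mg/L; × 2 = 0.30 mg/L, which is 3% of 10 mg/L. At D = 2 nothing is lost. At D = 2.5 it is 0.375 mg/L, or 3.75 points.
- *Relative, or already on the final scale.* Scaling adds nothing and the table in step 2 applies.

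**5. What is omitted under every reading**, unless the 3% was itself estimated on final dilution values: error in tube length and weighing, and variation between shots within a person. The protocol gives no figure for these, so I do not size them.

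**The case against.** A reader might infer that Group 2 cannot resolve 5% at all, or that its true figure is about 10% with power of about one third. The documents do not support that as a fact. It needs the 3% to be a constant error in points of injectate fraction on the mixed reading, with one reading per intervention. A relative error or one already on the final scale leaves the SD at 3, as does a share of the measuring range at D = 2. Quoting the 3% beside a dilution difference in per cent makes a final-scale meaning quite natural.

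Four further points have weight:

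- Section 3.5 collects four samples per intervention. If their mean is compared and reading errors are independent, 6/√4 = 3 points, which offsets the doubling at D = 2. Starting from 3, the SD would fall to 1.5. But the protocol does not say that the mean is compared, question (b) concerns change over time, and averaging four samples from one shot does not reduce shot-to-shot variation.
- Participant main effects cancel in within-person comparisons, so it would be wrong to charge the full between-person variation to this figure. Variation between shots, and participant-by-intervention variation, remain.
- If 3% were the SD of paired differences, the paired t at n = 8 would give 4.0% and power of 98%. The label is the fluorimeter's, however, not that of a difference.
- The normal formula is applied correctly, 8 is a minimum, and at n = 10 the t-based figures are below 5%.

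These points limit the size of the problem. They do not turn an instrument SD into the SD of the compared outcome, and they do not restore 90% power for single-sample comparisons at n = 8 when the final-scale SD is 3.

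**Conclusion.** The statement is wrong as written, by a modest amount that can be shown and a larger amount that is only conditional. Taking the 3% as the SD of a single final dilution value, the detectable difference at n = 8 is 5.2% (two-sample t) to 5.7% (paired t, SD of differences 3√2), and power for 5% is 87% to 81% rather than 90%. That is a best case, because it carries measurement error only. If the 3% is additive on a single mixed reading, the figures are 9.7% to 11.4% and 38% to 30% at D = 2, and worse for samples under 5 µL. Which applies cannot be decided from the protocol. For a pilot study this calls for an accurate restatement; it does not show that the design fails.

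**What to change.** In section 3.2, restate the Group 2 detectable difference for the back-calculated dilution using a paired t calculation. Say three things with it:

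1. The scale of the 3%: points, relative, or share of range, and whether before or after back-calculation.
2. Whether one sample or the mean of the four is compared.
3. That the figure is a measurement-error-only best case, excluding shot-to-shot variation, and whether the 3% already covers volume and weighing error.

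Until the scale is settled, the supportable wording for single-sample comparisons at n = 8 is at least 5.2% to 5.7%, rising to about 10% to 11% if the error is additive on the reading.

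No participants need be added. I would not prescribe weighting by 1/D²: it is justified only under the additive assumption, and because D depends on the volume collected it would tie the weights to an outcome of the trial.

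The cost is a rewording of one sentence and a less favourable stated figure.
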